7.2. ASSESSMENT OF ADVERSE EVENTS

The need to capture AEs is not dependent upon whether or not the clinical event is associated with the use of the study device or procedure. All AEs, regardless of severity, occurring at the index ablation through study exit visit must be recorded. Events occurring prior to the endovascular procedure must be listed in the medical history.

The following information should be obtained for each AE:

1. Event description. Every effort must be made to report the underlying condition or unifying diagnosis for the event. To avoid vague, ambiguous or colloquial expressions, the AE should be recorded in standard medical terminology rather than the subject's own words when possible. Signs and symptoms that are considered unrelated to an encountered syndrome or disease should be recorded as individual AEs on the CRF (e.g., if congestive heart failure and severe headache are observed at the same time, each event should be recorded as an individual AE).

In addition, AEs occurring secondary to other events (e.g., sequelae) should be identified by the primary cause (i.e., a "primary" AE, if clearly identifiable, generally represents the most accurate clinical term to record on AE CRF; events occurring secondary to the primary event should be described in the narrative description of the case [e.g., example: orthostatic hypotension \rightarrow fainting and fall to floor \rightarrow head trauma \rightarrow neck pain; the primary AE is orthostatic hypotension]).

2. Duration: The date of onset and date of resolution should be reported. Every effort should be made to capture the exact dates.

3. Outcome: The final status of the event should be reported as resolved, ongoing, or if it resulted in death. If the event is present at the final study visit, the ongoing box must be marked.

4. Severity: The worst severity of the event must be reported as mild, moderate, or severe using the following definitions:

- Mild: Aware of sign or symptom, but easily tolerated
- Moderate: Discomfort enough to cause interference with usual activity
- Severe: Incapacitating with inability to work or do usual activity

5. Action taken: Treatment of the event may be reported as none, medical and/or surgical.

6. Seriousness: Determined by using the criteria in Section 7.1.

7. Relationship to device (study device or ancillary device), and procedure. The relationship to device and study procedure will be assessed using the following criteria.

- Not related: no temporal association, or the cause of the event has been identified; or the device or procedure cannot be implicated
- Unlikely: the relationship with the use of the device seems not relevant and/or the event can be reasonably explained by another cause, but additional information may be obtained
- **Possible:** temporal association, but other etiologies are likely to be the cause; however, involvement of the device or procedure cannot be excluded
- **Probable**: the relationship with the use of the investigational device seems relevant and/or the event cannot reasonably be explained by another cause, but additional information may be obtained
- **Causal:** temporal association; other etiologies are possible, but unlikely

If any AE is considered to be "possibly related" or "related" to the use of the study device, that event will classed as an ADE or a SADE.

7.3. Reporting/Recording of AEs

Throughout the course of the study, all efforts will be made by the investigator to remain alert to possible AEs. The first concern will be the safety of the subject, and for providing appropriate medical intervention. The period of observation for collection of AEs starts at index ablation procedure until study exit. Any AE should be recorded on the appropriate study worksheet.

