After confirmation of the absence of atrial thrombus precluding catheter introduction, eligible subjects will undergo mapping and ablation. Subjects will be assessed for potential adverse events prior to discharge. Esophageal evaluation, and CT and/or MR imaging may optionally be performed after treatment or during follow-up.

Subjects will be followed for approximately 365 days after the ablation procedure to characterize safety and product performance. Note, the Day 10 visit can be conducted by telephone. Ambulatory monitoring for a minimum of 48 hours will be conducted within the follow-up windows at Day 90, Day 180, and Day 365. Use of antiarrhythmic drugs and other important cardiovascular drugs will be collected at every visit. Serious adverse events (AEs) will be collected starting on Day 0 through study exit.

A summary of the schedules of evaluations and visits can be found in Appendix 1.

5.3. Subject Population

Up to a total of 30 subjects meeting the following study entry criteria will be treated.

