5.4.4. VISIT 2: DAY 0 – INDEX ABLATION PROCEDURE

After documenting concomitant use of AADs and other important cardiovascular medications and confirming the absence of atrial thrombus or another abnormality precluding catheter introduction, catheters are introduced percutaneously and advanced to the chamber of interest. For left atrial procedures, if the esophagus is not mechanically deviated away from the left atrium, a temperature probe may be placed in the esophagus to monitor heating during the procedure.

The heart chamber is mapped using the Affera Sphere-9 Ablation Catheter and the Affera Mapping System to generate a representation of the heart and to locate the areas of the heart that are creating or propagating problematic electrical signals that interfere with the proper rhythm. In addition, pacing is used to identify the location of the phrenic nerve.

Ablation using the Affera Sphere-9 Ablation Catheter and the Affera RF Generator is performed, and data regarding ablation delivery is recorded by the Affera Mapping System. Procedural success is monitored by mapping and/or pacing to verify termination and non-inducibility of the arrhythmia (all subjects) and/or successful isolation of target pulmonary veins. Any serious procedural adverse events (AEs) will be documented.

Prior to discharge, the following will be documented:

- Vital signs
- 12-lead EKG
- Serious adverse events (AEs)

At the discretion of the investigator, the following assessments can be performed prior to discharge:

- Transthoracic echocardiography (TTE)
- Endoscopic evaluation of the esophagus
- CT or MR imaging

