5.4.5. VISIT 3: DAY 10 ± 3 DAYS (TELEPHONE CALL)

The following assessments will be performed, optionally via a telephone call:

- Concomitant use of AADs and other important cardiovascular medications
- Serious cardiovascular AEs

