Appendix 1. Schedule of Evaluations and Visits

SCHEDULE OF EVALUATIONS AND VISITS

	SCE	SCHEDULE OF EVALUATIONS AND VISITS	VALUATION	S AND V ISU			
Visit	Screening	Day 0 Ablation Procedure	Day 0 Discharge	Day 10 ± 3 days†	Day 90 ± 14 days	Day 180 ± 30 days	Day 365 ± 30 days
Visit Number	1	2	2	3	4	5	6
Informed Consent	>						
Demographics	>						
Medical History	>						
Concomitant Antiarrhythmic Drugs							
(AAD) and Other Important Cardiovascular Medications	>	>		>	>	>	>
Inclusion/Exclusion	>						
Physical Exam	>						
Vital Signs	>		>				
12 lead EKG	>		>		>	>	>
Hematology	>						
Urine Pregnancy Test*	>						
Transthoracic Echocardiography Exam	>		#				
Optional CT or MR imaging	**		*		**	**	**
Atrial thrombus screening		~					
Ablation		~					
Endoscopic Evaluation of Esophagus			#				
Serious Adverse Events		~	>	~	~	>	>
Ambulatory Monitoring (48 hours minimum)					>	>	>
* Women of child-bearing potential only							

Telephone call optional Optional procedure * #

CONFIDENTIAL

Affera Page 41 of 46

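### Sections 7.2 and 7.3 require every adverse event to be recorded, but the Synopsis, visit lists and Appendix 1 name only serious (or serious cardiovascular) events, so non-serious device effects could go unrecorded

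*Combined protocol and SAP*

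**What the plan says.** Section 7 sets a broad rule. Section 7.2 says "All AEs, regardless of severity, occurring at the index ablation through study exit visit must be recorded" and asks for severity, seriousness and relationship to device and procedure for each event. Section 7.3 gives the same period ("The period of observation for collection of AEs starts at index ablation procedure until study exit") and adds "Any AE should be recorded on the appropriate study worksheet".

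The sections that tell a site what to do at each visit are narrower:

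- The Synopsis and Section 5.2 share the sentence "Serious adverse events (AEs) will be collected starting on Day 0 through study exit".
- Section 5.4.4, on the procedure, says "Any serious procedural adverse events (AEs) will be documented". Its pre-discharge list also names serious events.
- Sections 5.4.5 to 5.4.8 (Day 10, 90, 180 and 365) list "Serious cardiovascular AEs".
- Appendix 1 has one adverse event row, "Serious Adverse Events", marked from the procedure through Day 365.

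Two items carry no seriousness limit. Section 5.2 says "Subjects will be assessed for potential adverse events prior to discharge", and Section 5.5.2 lists an AE assessment for subjects who withdraw, where possible.

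**The concern.** The protocol gives two recording scopes for the same period. A coordinator who completes forms from the visit lists and Appendix 1 is prompted for serious events, and from Day 10 for serious cardiovascular ones. A coordinator who starts from Section 7.2 records everything.

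This is an initial assessment of a new electrode design in up to 30 patients, with descriptive analysis only. Section 7.1 defines an adverse device effect (ADE) as any device-related adverse event, with the serious subset (SADE) defined separately. If non-serious events are captured only when a site happens to follow Section 7.2, an ADE count has no clear meaning.

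There is a second effect. Section 7.4 makes the sponsor responsible for classifying adverse events. Under the visit lists, the site decides whether an event is serious before anything is recorded, so an event it judges non-serious may never reach the sponsor for review.

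**Working it through.** The protocol states no figure on this point, so the check is a comparison of text.

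**1. Scope by place**

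| Place | Scope named |
|---|---|
| 7.2, 7.3 | All adverse events, index ablation to exit |
| Synopsis, 5.2, 5.4.4, Appendix 1 | Serious adverse events |
| 5.4.5, 5.4.6, 5.4.7, 5.4.8 | Serious cardiovascular adverse events |
| 5.2 (pre-discharge check), 5.5.2 (withdrawal) | Adverse events, no limit stated |

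Two sections require everything, four places name serious events, and four visit sections are narrower still. All of this is current text.

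**2. Can Section 7.2 be read as serious events of any severity?** No. It records severity (item 4: mild, moderate, severe) and seriousness (item 6: by the criteria in 7.1) as separate fields. A seriousness field would have no use if only serious events were entered.

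**3. Does anything depend on non-serious events?** Yes. Section 7.1 does not require seriousness for an ADE, and the end of 7.2 sorts device-related events into ADE or SADE. Under serious-only collection, the non-serious ADE class would be empty by construction.

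**4. Non-serious examples from the anticipated list in 7.5, followed through each route**

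| Event, if not serious | Under 7.2/7.3 | Under visit lists and Appendix 1 | Other route |
|---|---|---|---|
| Skin burn, local hematoma, chest discomfort | Recorded as AE | Not prompted | No dedicated test or finding field |
| Pericardial effusion on pre-discharge TTE | Recorded as AE if clinically significant (7.1) | Not prompted as AE | 6.2.2: recorded as CS or NCS, if the TTE is done |
| Esophageal ulcer on endoscopy | Recorded as AE if clinically significant (7.1) | Not prompted as AE | 6.2.6: recorded as CS or NCS, if the endoscopy is done |

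In the last two rows the finding is kept, but without AE severity, seriousness or relatedness.

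**5. Effect on defined outcomes.** The primary safety outcome in 8.2.1 is a rate of listed serious events. Limiting collection to serious events removes none of them by definition. Section 8.3 names no ADE or SADE table, so the effect falls on the general safety description.

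**The case against.** The best defense is that the visit lists are minimum prompts and Section 7 governs. Section 7.2 is the dedicated section and is mandatory in tone, 7.3 repeats it, and no passage says that non-serious events are excluded. Section 5.2 has an unrestricted check before discharge and 5.5.2 has one at withdrawal. This reading is reasonable, but the protocol does not state it. The two unrestricted items leave the visit lists and Appendix 1 as they are, so non-serious events can still be missed.

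Two stronger readings are tempting and should not be drawn.

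- A reader might infer that the early signal for the severe events is lost: ulcer before fistula, effusion before tamponade. The documents do not support this. Sections 6.2.2 and 6.2.6 require abnormalities on TTE and endoscopy to be recorded whenever those tests are done. Section 6.2.1 does the same for clinically significant EKG abnormalities.
- A reader might infer that the safety table would probably be empty. The Introduction cites a 2-3% complication rate, which gives 30 × 0.02 = 0.6 to 30 × 0.03 = 0.9 expected complications, and a chance of none of 0.98^30 = 55% to 0.97^30 = 40%. But that rate is for AF ablation, flutter patients are also enrolled, and the SAE definition in 7.1 covers events of any cause over a year of follow-up. It says nothing reliable about an all-cause SAE table.

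**Conclusion.** The inconsistency is real and worth correcting, as a should-fix matter of internal consistency. Sections 7.2 and 7.3 conflict in scope with eight other places (four naming serious events, four naming serious cardiovascular events), and non-serious device effects can go unrecorded from Day 0 onward.

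The primary safety outcome is not directly changed. The damage is to the wider safety objective in 5.1 and to any count of non-serious ADEs, where a zero could not be interpreted. Its size cannot be quantified: the documents give no rate for non-serious events and do not show which section the site or the case report forms follow. The conclusion assumes only that a site may reasonably work from the visit lists and Appendix 1. If the case report forms already prompt for all adverse events, the practical risk is smaller, but the text still needs to agree.

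**What to change.** Let Section 7.2 govern and carry one scope throughout:

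- Appendix 1: rename the row to Adverse events (all; seriousness per 7.1), marked from Day 0 through Day 365.
- Synopsis, 5.2 and 5.4.4: replace serious adverse events with all adverse events.
- 5.4.5 to 5.4.8: replace serious cardiovascular AEs with all AEs. If these four sections are left alone, the conflict persists from Day 10 onward.
- Case report forms: align them to the same scope.
- Imaging and endoscopy: enter clinically significant findings as adverse events, in line with 7.1. Findings graded not clinically significant stay as test findings.
- Section 8.3: add separate tabulations of ADEs and SADEs.

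The cost is wording changes and modest extra data entry for at most 30 subjects at one site. No new visit, test or procedure is needed.

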7.5. ANTICIPATED ADVERSE EVENTS

Anticipated complications/AEs are defined as complications/events that can be reasonably associated with catheter ablation procedures.

Anticipated AEs include, but are not limited to:

- Air embolism
- Allergic reaction (including anaphylaxis)
- Anesthesia reaction
- Angina
- Aorto-right atrial fistula
- Arrhythmias, including exacerbation of pre-existing atrial fibrillation
- Arterial-venous fistula
- Cardiac perforation/ tamponade
- Cardiac thromboembolism
- Cardiac or respiratory arrest
- Catheter entrapment

- Cerebrovascular incident / Stroke
- Chest pain/discomfort
- Congestive heart failure
- Coronary artery dissection
- Coronary artery spasm
- Coronary artery thrombosis / occlusion
- Death
- Diaphragmatic paralysis
- Dislodgement of ICD or permanent pacing leads
- Endocarditis
- Esophageal ulceration
- Gastroparesis
- Heart failure / pump failure
- Hemoptysis
- Hemoptysis
- Hemothorax
- Hypotension
- Hospitalization (initial and prolonged)
- Increased creatinine phosphokinase (CPK) level
- Infections
- Laceration
- Leakage of air or blood into the lungs or other organs due to perforation
- Left atrial esophageal fistula
- Major bleeding, requiring surgery or transfusion
- Myocardial infarction
- Obstruction or perforation or damage to the vascular system
- Pericarditis
- Pericardial effusion
- Phrenic nerve damage including Diaphragmatic paralysis
- Pleural effusion
- Pneumonia
- Pneumothorax
- Pulmonary edema
- Pulmonary embolism
- Pulmonary vein dissection
- Pulmonary vein thrombus
- Pulmonary hypertension
- Respiratory depression
- Skin burns
- Severe PV stenosis or complete occlusion, even asymptomatic
- Tamponade, potentially requiring surgery
- Temperature elevation or fever
- Transient Ischemic Attack (TIA)
- Thromboembolism

- Thrombosis
- Unintended complete or incomplete AV, Sinus node, or other heart block or damage
- Valve damage
- Vascular bleeding / local hematomas / ecchymosis
- Vasovagal reactions
- Ventricular tachyarrhythmia
- Volume overload

7.6. **DEVICE DEFICIENCIES**

Device deficiency is defined as an inadequacy of a medical device with respect to its identity, quality, durability, reliability, safety or performance.

Note, device deficiencies include malfunctions, use errors, and inadequate labelling. All device deficiencies or malfunctions that occur during the course of the trial and could have led to an SAE must be reported, whether or not they were associated with an AE.

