8.2. STUDY OUTCOMES

8.2.1. SAFETY

The primary safety outcome is the rate of the following SAEs occurring starting Day 0 and extending through the Day 10 follow-up visit:

- TIA
- CVA
- Major bleeding
- Cardiac tamponade
- Pulmonary vein stenosis
- Severe pericarditis requiring hospitalization
- Myocardial infarction
- Diaphragmatic paralysis
- Atrio-esophageal fistula (through the Day 90 assessment)
- Valvular damage
- Phrenic nerve palsy
- Intra-procedural device complications requiring open chest or heart surgery
- Vascular complications requiring surgical intervention
- Death

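### The rule that records a secondary adverse event under its primary cause has no exception for the primary safety events, so a listed stroke, infarction or major bleed could go uncounted

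*Combined protocol and SAP*

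**What the plan says.** Section 7.2, item 1 (Event description), sets the recording rule for chains of events: "AEs occurring secondary to other events (e.g., sequelae) should be identified by the primary cause". It says that the primary AE, "if clearly identifiable, generally represents the most accurate clinical term to record on AE CRF". Of the rest of the chain it says that "events occurring secondary to the primary event should be described in the narrative description of the case". Its worked example runs from low blood pressure on standing, through a faint and fall, to head trauma and neck pain, and concludes that "the primary AE is orthostatic hypotension". The head trauma gets no term of its own.

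The remaining items of 7.2 (dates of onset and resolution, outcome, severity, action taken, seriousness, relationship) are collected for each AE.

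Section 8.2.1 defines the outcome: "The primary safety outcome is the rate of the following SAEs occurring starting Day 0 and extending through the Day 10 follow-up visit". A closed list follows, which includes TIA, CVA, major bleeding, cardiac tamponade, myocardial infarction and death. Atrio-esophageal fistula is followed to the Day 90 assessment. Neither 7.2 nor 8.2.1 mentions the other.

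**The concern.** The recording rule favours the start of a causal chain, while the primary safety outcome is built largely from end events. Section 7.5 anticipates several events that can start such a chain but are not in 8.2.1, for example air embolism, "Coronary artery spasm", "Coronary artery thrombosis / occlusion" and laceration. A site that applies 7.2 as written can enter one of these as the AE and leave the stroke, infarction or bleed in free text.

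At stake is the trial's main safety figure. An event that exists only in a narrative has no required onset date, although the outcome is limited to a time window, and no seriousness entry, although the outcome counts only serious events. Replacing a listed event by an unlisted cause can lower the rate but never raise it. The study is small and expects few events, so a single one matters to what is reported.

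**Working it through.** The plan states no hypothesis, threshold or derived sample size (8.1), so there is no figure of its own to reproduce. The check compares the sections and then gives the scale.

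**Step 1: apply the 7.2 rule to chains made of events that the protocol itself names.**

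| Initiating event (7.5) | In the 8.2.1 list? | End event (8.2.1) | AE term under 7.2, item 1 | Where the end event goes |
|---|---|---|---|---|
| Air embolism | No | TIA or CVA | Air embolism | Narrative |
| Coronary artery spasm, or thrombosis/occlusion | No | Myocardial infarction | The coronary event | Narrative |
| Laceration | No | Major bleeding | Laceration | Narrative |

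In each row the term on the CRF is not a component of the outcome.

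**Step 2: look for text that would bring the end event back.**

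- 7.2 requires all AEs to be recorded but does not say that a secondary one keeps its own term. Item 1 points the other way.
- 7.4 requires all SAEs to reach the sponsor and the CRO within 24 hours, and makes the sponsor responsible for evaluation and classification. It gives no rule for extracting 8.2.1 components from narratives. Its provision for querying the site applies when there is too little information for a definitive diagnosis, which a clearly identified primary cause need not trigger.
- 8.3 gives generic frequency summaries and no counting rule for this outcome. No adjudication step is described.
- Death is less exposed: 7.2, item 3, records it as an event outcome, and 7.4 puts its cause and device relationship on the AE form.

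**Step 3: scale.** Inputs: n = 30, the maximum treated (5.3), and a complication rate p of 2-3% (Introduction).

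- Effect of one missed event: 1/30 = 3.3 percentage points.
- One event, one missed: 1/30 = 3.3% (exact Clopper-Pearson 95% interval 0.1-17.2%) becomes 0/30 = 0% (0-11.6%).
- Two events, one missed: 2/30 = 6.7% (0.8-22.1%) becomes 1/30 = 3.3% (0.1-17.2%).
- Expected events: 30 × 0.02 = 0.6 and 30 × 0.03 = 0.9.
- Chance of at least one: 1 − 0.98^30 = 45% and 1 − 0.97^30 = 60%.

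Let f be the share of events that have a clearly identifiable unlisted cause and are not recovered under 7.4. The documents give no value for f. The expected loss is 30 × p × f: zero at f = 0, and at most 0.6 to 0.9 events at f = 1. At an assumed f of 0.1 it is 0.06 to 0.09; at an assumed 0.5 it is 0.30 to 0.45.

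**The case against.** The strongest reply has four parts.

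- **The rule is soft.** It is worded with should, generally and a condition that the primary cause be clear. It does not say that only the initiating event may be recorded. This stands, and it limits the claim to what can happen. It does not remove the problem, because the instruction and its example both lead to a single term.
- **The outcome is defined by events occurring.** A reader might infer that a site following 7.2 necessarily removes true outcome events from the coded data behind the rate. The documents do not support that. They describe no coding step, and they do not say that the rate is taken from CRF terms. A stroke told in a narrative has still occurred and meets the definition. The loss is conditional on counting from AE terms.
- **Safeguards exist.** A stroke or infarction would ordinarily be an SAE in its own right, reported within 24 hours and reviewed by the sponsor. At one center with up to 30 subjects, every narrative can be read. Recovery is plausible, but it is not required.
- **The examples are selective.** Section 7.5 also lists stroke, TIA, infarction and major bleeding as events in themselves, so the protocol plausibly expects them as recordable terms. A vascular complication that needs surgery is already a component. Esophageal ulceration leading to fistula is a weaker example, since endoscopy is optional and the ulcer might never be known. Nothing shows that listed events typically follow unlisted causes.

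It is also fair that the 2-3% is a general figure from a paragraph on AF ablation, not the rate of the 8.2.1 list, and that no prespecified decision depends on 1/30 against 0/30.

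**Conclusion.** The concern holds as a gap between two stated rules. Section 7.2, item 1, can leave a listed TIA, CVA, infarction or major bleed without its own term, onset date and seriousness, and no section exempts it or requires its recovery. Undercounting is possible, not certain. It needs three things together: a clearly identifiable cause outside the list, a site that applies the rule, and a count made from AE CRF terms without a reading of the narratives.

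If it happens, the direction is fixed downward, and the size is 3.3 percentage points per missed event at full enrollment. With fewer than 30 treated, each event weighs more. The 0.6 to 0.9 expected events are a ceiling for illustration, because only the fraction f of them could be lost. The reported safety rate would change; no formal test would, as the plan has none. This merits correction because the remedy is cheap and the primary safety rate should not depend on recovery that the plan does not prescribe.

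**What to change.** Add an exception to 7.2, item 1, and repeat it in the CRF completion guide. Suggested wording: *Any event listed in 8.2.1 is recorded as its own AE, with its own onset date and seriousness, even when it is secondary to another event. It is linked to the causal AE and is counted in the primary safety outcome.*

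The general primary-cause rule can stay for all other events. Sample size, visits and patient care are unaffected. The cost is a sentence in each document, a few extra AE lines, and possibly a slightly less favourable safety rate.
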